Low back (average over past 24 hours and worst pain over 24 hours) and leg pain (average leg pain in left and right legs, individually over the past 24 hours) VAS evaluations will also be taken using e-diaries during the same 14 day period where pain medication usage is being collected. The VAS scores will be collected every day for the 14 day period with at least evaluations for 7 days. If more than 7 days of VAS scores are collected the last 7 days' scores will be used to calculate the average pain over a week.

Note: Low back and/or leg pain may generally be considered an adverse event and used in the evaluation of treatment safety. In this study, however, low back pain is also evaluated as an efficacy endpoint. Section 7.3 provides further details on how AEs of low back pain are defined.

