6.7.6 Post-Treatment Pain Medication Usage Collected by E-Diary

For collection of post-treatment pain medication use, subjects should be contacted by either IWRS or by the site, approximately 2 weeks prior to each post-treatment visit as a reminder to complete daily pain medication e-diaries for 2 weeks during the 30 days prior to each follow-up

visit other than for the 1 month visit that must be collected during the 14 days prior to the scheduled visit. At least 10 daily entries out of a possible 14 should be available at each study visit. Otherwise, absence of more than 4 entries will be considered a protocol deviation. Based on the opioid information entered into the e-diary during the 2 weeks prior to each post-treatment visit, it will be determined if subjects have shifted from baseline. Category shifts in opioid usage will be defined as:

CONFIDENTIAL

It is strongly recommended that there be no changes (increase or decrease) from or additions to baseline pain medications (opioids, NSAIDs, aniline analgesics, etc.) for at least the 24 month primary efficacy and safety follow-up period.

This is designed to minimize possible confounding treatment effects of alterations in pain medications. Furthermore, it is suggested that subjects do not schedule any medical procedures during the 2 weeks prior to any study visit which would require an adjustment in pain medications. However, should a significant increase in pain from baseline occur, the subject

CONFIDENTIAL

should be provided appropriate pain relief and an adverse event documented. Should there be any deviation from the baseline dose, information regarding the deviation must be documented.

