7. SAFETY GUIDANCE

7.1 Definitions

7.1.1 Adverse Event

According to the International Conference of Harmonization [ICH] guideline for Good Clinical Practice, an AE is any untoward medical occurrence in a patient administered a pharmaceutical product and which does not necessarily have a causal relationship with this treatment. An AE can therefore be any of the following:

- Unfavorable and unintended sign (including an abnormal laboratory finding), symptom, or disease temporally associated with the use of a medicinal (investigational) product, whether or not considered related to the medicinal (investigational) product.
- Any new disease or exacerbation of an existing disease (a worsening in the character, frequency, or severity of a known condition)
- Recurrence of an intermittent medical condition (e.g., headache) not present at baseline
- Any deterioration or abnormality in a laboratory value or other clinical test (e.g., ECG, X-ray) that is associated with symptoms or leads to a change in study treatment or concomitant treatment or discontinuation from study drug
- Adverse events that are related to a protocol-mandated intervention, including those that occur prior to assignment of study treatment (e.g., screening procedures such as biopsies etc.).

Adverse events will be captured following signing of the informed consent form. Pre-existing conditions (i.e., medical history) which **worsen** during a study are to be reported as AEs.

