7.3 Adverse Events of Special Interest – Back Pain

Low back pain may generally be considered an adverse event and used in the evaluation of treatment safety. In this study, however, low back pain is also evaluated as an efficacy endpoint. Pain data provided on the low back pain VAS will not routinely be considered an adverse event in this study. If a subject reports an adverse event of low back pain, the following information will be collected from the subject:

- 1. Whether or not the pain is of increased intensity from baseline
- 2. Whether or not there is an increased frequency of pain, regardless of intensity, as compared to baseline
- 3. Whether or not the pain is in a different location in the lower back as compared to baseline
- 4. Whether the symptoms required an unscheduled visit
- 5. The subject's assessment of the cause of the event, if any specific cause is suspected.

A back pain AE should be reported if the subject answers yes to questions 1-4 above. If a back pain AE is reported, the subject's assessment of the cause of the event should also be recorded if any specific cause is suspected.

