9.7.1 Primary Safety Endpoint

Evaluation of overall safety, which includes the following:

- Subject reported AEs and SAEs from baseline through 24 months post-treatment, including adverse events of special interest (i.e., AEs of worsening low back pain)
- Laboratory tests (hematology, serum chemistry, inflammatory markers and antibody analysis). Abnormal results will be assessed relative to normative ranges and shift tables from baseline through 24 months post-treatment
- Reported events from radiographic imaging from baseline through 24 months posttreatment, including disc height at the treated level
- Post-treatment interventions affecting the treated disc through Visit 8 (24 months posttreatment) (comparison of the proportion of subjects in each group with an adjudicated post-treatment intervention at the treated level, and the proportion of subjects in each group with an adjudicated post-treatment intervention any lumbar level)
- Vital signs (heart rate, blood pressure and temperature) and body measurements (height, weight and BMI)
- Physical examinations (abbreviated).
- Neurological examinations (motor, sensory, reflex).

[figure not shown]
Descriptive statistics will be used for the summary of safety parameters – the number and percentage will be used for the incidences of AE/SAEs, deaths, early discontinuation due to AEs, and post-treatment interventions. The AE/SAE severity and relationship with the study procedure and treatment will be summarized and presented.

The mean, standard deviation/error, minimum, median, and maximum will be used for the laboratory parameters. The shift table (cross-tabulation) for the changes from baseline (low/normal/high) for the laboratory parameters will also be also provided and the test for treatment difference.

[figure not shown]
Safety parameters of special interest (i.e., AEs of worsening low back pain) will be summarized through 24 months post-treatment by treatment arm, severity, and the time from the study injection to the start of the AEs (0 to \leq 7 days, >7 days to < 3 months, \geq 3 months to 24 Months).

The incidence of this special interest AE (worsening low back pain) occurring within 3 to 24 months after study treatment will be also summarized, by treatment arm, for the responders and non-responders of the Primary Efficacy Endpoint.

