The actual low back pain VAS score, the changes from the baseline and the responders with at least 50% reduction of low back pain VAS score at the time which the AEs of low back pain occurs will be summarized for each treatment, and the subject data listing will be presented for clinical review and assessment. Shift tables of changes in opioid use from the baseline to the time of AE onset will be also presented.

CONFIDENTIAL

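### Section 7.3 does not say whether one yes or four yeses make a back pain AE, so sites could record the adverse event of special interest inconsistently or too rarely

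*Combined protocol and SAP*

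**What the plan says.** Section 6.7.2 sends the reader to 7.3 for the definition: "Section 7.3 provides further details on how AEs of low back pain are defined". Section 7.3 first says that VAS pain data will not routinely count as an AE. For a subject who reports low back pain as an AE, it then lists four items to collect: increased intensity; increased frequency, whatever the intensity; location ("Whether or not the pain is in a different location in the lower back as compared to baseline"); and visit ("Whether the symptoms required an unscheduled visit"). The subject's own view of the cause is a fifth item. The reporting rule is: "A back pain AE should be reported if the subject answers yes to questions 1-4 above".

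Three other sections bear on the same event:

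- Section 7.1.1 counts as an AE any exacerbation of an existing disease, described as "a worsening in the character, frequency, or severity of a known condition". It adds that pre-existing conditions which worsen are to be reported.
- Section 6.7.6 says that a subject with a significant increase in pain from baseline "should be provided appropriate pain relief and an adverse event documented".
- Section 3.1 also provides for pain relief after a significant increase in pain, and there ties the increase to a VAS score above baseline.

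Section 9.7.1 places these events in the primary safety endpoint, "including adverse events of special interest (i.e., AEs of worsening low back pain". They are tabulated by arm, severity and time from injection. For months 3 to 24 they are also shown by responder status.

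**The concern.** The rule names four questions and gives no connective. Elsewhere the protocol supplies one: section 7.5 asks for one or more conditions, while 6.4.6 and 4.2.1 ask for all. Up to 45 sites apply 7.3 when they decide whether to record an event.

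Taken literally as all four, the rule needs pain that is more intense, more frequent, in a new place, and serious enough to have required an unscheduled visit. Worsening at the usual site fails question 3, and worsening handled at a scheduled visit fails question 4. At stake are the completeness and consistency of the one AE category singled out as of special interest. The VAS and responder summaries that 9.7.1 attaches to these events are taken "at the time which the AEs of low back pain occurs will be summarized for each treatment", so they describe recorded events and cannot recover one that was never recorded.

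**Working it through.** The documents give no rate or count for this AE category under 7.3, so there is no figure to reproduce. The check is a comparison of texts plus a count of answer patterns.

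**Comparison on one case.** Suppose that at a scheduled visit a subject reports that the usual pain, in the usual place, is more intense and more frequent than at baseline, and is given pain relief. The answers are question 1 yes, question 2 yes, question 3 no, question 4 no.

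- 7.1.1: an AE, because severity and frequency have worsened and either is enough.
- 6.7.6: an AE is to be documented, provided the increase is judged significant. No condition on location or type of visit is set.
- 7.3 read as any: an AE is reported.
- 7.3 read as all four: no AE is called for, because questions 3 and 4 are no.

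Under any, the three sections agree. Under all four, 7.3 departs from the other two.

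**Count of answer patterns.** The only input is the four yes/no items in 7.3.

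- All patterns: 2^4 = 16. Any reports 16 − 1 = 15; all four reports 1. The readings disagree on 15 − 1 = 14 and agree on 2 (no yes at all, and four yeses).
- Patterns with more intense pain (question 1 yes): 2^3 = 8. Any reports 8; all four reports 1.
- Patterns with more intense or more frequent pain (question 1 or 2 yes): 16 − 2^2 = 12. Any reports 12; all four reports 1.

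These are counts of possible answers. They show that the readings are far apart in logic, but not how often real reports fall where they differ. That would need the joint frequency of the four answers, which the documents do not give.

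**Sections 3.1 and 6.7.6 together.** If a significant increase means a VAS score above baseline (3.1), and a significant increase calls for an AE (6.7.6), then a raised VAS score alone could be taken to require an AE. Section 7.3 says VAS data will not routinely be one. A correction confined to 7.3 would leave this second inconsistency in place.

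**The case against.** The best reply is that the text of 7.3 points away from the harmful reading. Question 2 asks about frequency irrespective of intensity. If all four answers had to be yes, increased intensity would already be compulsory through question 1 and that qualifier would do nothing. Questions 1 to 3 also resemble the either/or list in 7.1.1. This stands: any is the more natural reading and probably the intended one. It does not remove the problem, because the literal wording still permits all four and no readable section settles it.

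A reader might infer that under all four, worsening at the usual site would not be counted at all. The documents do not support that. Sections 7.1.1 and 6.7.6 call for an AE independently, 7.3 says if rather than only if, and 9.7.1 describes the category as AEs of worsening low back pain without tying it to the four questions. The loss arises only where a site lets 7.3 override the other two sections. The text does not say which governs.

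A reader might also infer that worsening would go unseen. It would not. Back pain VAS is taken from every subject at each scheduled post-treatment visit, with mean change reported by arm. Opioid shifts from baseline are determined at those visits, and interventions are compared within the primary safety endpoint. Sustained worsening by arm would show there, though none of these replaces AE incidence.

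Finally, a reader might size the effect from the Phase 2 figure of 27% in section 1.6.3. That figure belongs to the 18-million-cell dose, which is not used here. For saline, HA and 6 million cells the figures are 0%, 5% and 3%. All are reports within 7 days of injection, and nothing shows that they were defined by these four questions.

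**Conclusion.** The point holds as an ambiguity in a reporting instruction, one worth correcting because the count feeds the primary safety endpoint. Sites could record back pain AEs inconsistently, or too rarely where all four is applied and treated as overriding 7.1.1 and 6.7.6. An event not recorded would be absent from the special-interest table.

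The size is unknown; the 14 of 16 disagreement measures the gap in wording only. The documents give no basis for claiming bias between arms, since randomization is stratified by site and site staff who assess subjects are blinded. The primary efficacy analysis is not touched.

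The conclusion rests on the readable text. Section 7.3 shows no visible gap, but part of 6.7.6 is removed, and eCRF instructions, site training or SAP detail not available here may already state the rule. If so, 7.3 needs only to be brought into line with them.

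**What to change.** - In 7.3, report a back pain AE if the subject answers yes to any of questions 1 to 4.
- In 6.7.6 and in 3.1, add that the AE is assessed and recorded under 7.1.1 and 7.3, and that a VAS score above baseline is not by itself an AE.
- Keep the four answers for every back pain report, so that a stricter subset, such as events with four yeses, can be shown beside the main table.

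If all four was intended, 7.3 should say so. It should also state that worsening which meets only 7.1.1 or 6.7.6 is still reported as an AE, and whether it belongs in the special-interest category.

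The cost is a word or two in 7.3 and one clause in each of two other sections. No new visit or data item is needed, because 7.3 already collects the four answers; the stricter subset would be one optional extra table. The downside is that more minor back pain AEs may be recorded, including the pain that section 7.2 expects within 14 days of the procedure. The stricter subset and the existing split by severity and onset window let a reader separate these.

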7.4 Treatment and Follow-up of AEs and SAEs

AEs and SAEs, especially those for which there is an established relationship to investigational product, should be followed up until they have returned to baseline status, stabilized, or the follow-up period is complete.

If after the follow-up period, return to baseline status or stabilization cannot be established an explanation should be recorded on the eCRF.

7.5 Laboratory Test Abnormalities

Laboratory test results will appear on electronically produced laboratory reports directly from the central laboratory. Local laboratory results should be recorded on the eCRF, if applicable.

Any laboratory result fulfilling the criteria for an AE or SAE should be recorded on the eCRF and reported to the designated responsible parties in safety accordingly. The preference is to report a diagnosis rather than the laboratory value as the adverse event. However, if a diagnosis has not been confirmed, a clinically significant laboratory value should be reported including a modifier (e.g., worsening, increased, decreased) until a final diagnosis can be reported.

Any treatment-emergent clinically significant abnormal laboratory result is defined as meeting one or more of the following conditions:

- Accompanied by clinical symptoms
- Requiring a change in concomitant therapy (e.g., addition of, interruption of, discontinuation of, or any other change in a concomitant medication, therapy or treatment).

This applies to any protocol and non-protocol specified safety and efficacy laboratory result from tests performed after informed consent form signature, which fall outside the laboratory reference range and are considered clinically significant by the investigator. This does not apply to any abnormal laboratory result which falls outside the laboratory reference range but which does not meet the criteria for clinical significance (these will be analyzed and reported as laboratory abnormalities).

In the event of clinically significant abnormal laboratory test values, the tests should be repeated and followed up until they have returned to the normal range and/or an adequate explanation of the abnormality is found. If a clear explanation is established, it should be recorded on the eCRF.

7.6 Unblinding

The study blind should not be broken except in a medical emergency and only where knowledge of the test material received would affect the treatment. In an emergency, the investigator can obtain treatment assignment of any subject at their study center by contacting the medical monitor. If an emergency un-blinding becomes necessary, the investigator should notify the CRA or medical monitor, as soon as possible.

In the event treatment assignment needs to be provided to any blinded member of the sponsor study team, it must be done in accordance with the pre-specified blinding plan to ensure that bias is not introduced.

Importantly, all unblinded individuals will be specifically instructed to refrain from discussing any potentially unblinding information with either the subject or any blinded site, sponsor, or CRO personnel involved in the trial.

8. **REPORTING ADVERSE EVENTS AND SERIOUS ADVERSE EVENTS**

8.1 Reporting of Serious Adverse Events [Immediately Reportable]

All SAEs (as described in Section 7) that occur after the subject has signed informed consent (including the protocol-defined follow up period), regardless of judged relationship to investigational product, or after the study period, if considered serious and related to investigational product or to the subject's participation in the study, must be reported to the sponsor or designee within 24 hours of the investigator's knowledge of the event. All subjects with an SAE must be followed up and the outcomes reported until the event has returned to baseline status or stabilized. In the event of an SAE, the investigator must immediately notify sponsor or designee. SAE reporting will originate in the electronic data capture (EDC) system and an email will be sent to the designated responsible parties in safety.

The paper SAE form is in place as a back-up in the rare event that EDC is not accessible to the reporter of the SAE:

- •
- Provide copy of all relevant source documents, including medical history, hospital records and discharge summaries, and concomitant medications pages, as appropriate.

All SAEs that are considered unexpected, according to the Investigator's Brochure (IB), and related to the investigational medicinal product will be reported by the sponsor or its designee as an expedited 15-day report to the regulatory authorities as applicable and to all participating investigators.

Fatal or life-threatening suspected adverse reactions that are considered unexpected according to the IB and related to investigational product will be reported by the Sponsor or its designee to the regulatory authorities as applicable, and to all participating investigators as an expedited 7-day report.

Each investigator must notify the IRB/EC responsible for reviewing the study at their site of all 15-day or 7-day safety reports required by local regulations or IRB/EC requirements and shall provide the sponsor or its designee with written confirmation of said IRB/EC notification.

This study will comply with all local regulatory requirements and adhere to the full requirements of ICH Guideline for Clinical Safety Data Management, Definitions and Standards for Expedited Reporting, Topic E2.

8.2 **Procedures for Reporting Pregnancies**

All pregnancies that occur during the study are to be reported within 24 hours to the individual identified in the clinical study personnel contact information section of this protocol, and the investigator must provide sponsor or designee, by facsimile, a signed pregnancy tracking form. If a subject becomes pregnant during the study, the subject will remain in the study and only the requirement for radiation (x-ray or MRI) should be removed. All subjects who become pregnant will be monitored to the completion or termination of the pregnancy, including perinatal and neonatal outcome. Monitoring of the subject should continue until conclusion of the pregnancy. If the pregnancy is associated with an SAE (e.g., hemorrhage, spontaneous abortion), in addition to the Pregnancy Form, a separate SAE form must be provided as described in Section 8.1.

If a subject becomes pregnant during the study, the subject will remain in the study and only the requirement for radiation (x-ray or MRI) should be removed.

8.3 Expedited Reporting to Health Authorities, Investigators, IRBs, and ECs

The sponsor will promptly evaluate all SAEs and non-serious AEs of special interest against cumulative product experience to identify and expeditiously communicate possible new safety

findings to investigators, IRBs, ECs, and applicable health authorities based on applicable legislation.

To determine reporting requirements for single adverse event cases, the sponsor will assess the expectedness of these events using the current Investigator's Brochure.

The sponsor will compare the severity of each event and the cumulative event frequency reported for the study with the severity and frequency reported in the applicable reference document.

Reporting requirements will also be based on the investigator's assessment of causality and seriousness, with allowance for upgrading by the sponsor as needed.

9. STATISTICAL CONSIDERATIONS

9.1 General Considerations

The statistical analysis plan (SAP) will be finalized and submitted to the appropriate health authorities before any interim analysis or unblinding occurs. The primary unblinded statistical analyses will be conducted by the sponsor or authorized representative after all enrolled study subjects who remain active in the trial at the time of their 24 month study visit have completed this milestone event.

Interim analyses may be performed during the course of the trial. These will be conducted by external independent statistician(s) who will be unblinded to study data. All blinded personnel and subjects will remain blinded to the results of the analyses. The integrity of the study database will be maintained as well, and no bias will be introduced to the evaluations in the study due to the conduct of these interim analyses.

The details of interim analyses are outlined in the Statistical Analysis Plan (SAP). All subjects, independent reviewers and blinded personnel interacting with subjects will remain blinded through the completion of the study.

[figure not shown]
The primary efficacy objective of the study is to demonstrate that either rexlemestrocel-L alone or rexlemestrocel-L + HA has a higher rate of treatment success—defined as 50% reduction in low back pain VAS score, 15 point decrease in ODI score, and no interventions at the treated disc—compared to the saline control arm at 12 *AND* 24 months post-treatment. The significance level for the Primary Efficacy Endpoint is adjusted for multiple comparisons of each active

treatment arm to the control group. The family-wise type I error rate will be controlled below one-sided 0.025. Additional details, including the adjusted threshold for primary analysis success, will be finalized in the SAP.

For secondary endpoints, a gatekeeping strategy will be used to maintain the overall type 1 error at overall one-sided 0.025. For all other exploratory efficacy endpoints, the significance level of two-sided 0.05 will be used for comparison between each active arm and the control group.

